5.0 Study Design

As background for the statistical methods presented below, this section provides an overview of the study design. This overview is a summary only. The protocol is the definitive reference for all matters discussed in what follows.

This randomized, double-blind, dose response pilot study will examine the safety and efficacy of MDMA-assisted psychotherapy in subjects diagnosed with chronic, treatment-resistant PTSD of at least six months duration. Stage 1 will include two blinded and one open-label MDMA-assisted psychotherapy session scheduled approximately one month apart with a male/female co-therapist team. There will also be a moderate course of preparatory and integrative psychotherapy sessions as described in the Time and Events Table.

Upon enrollment, subjects will be randomly assigned to receive either active dose 1 (12 subjects), active dose 2 of MDMA (nine subjects), or comparator dose (five subjects). In Stage 1, subjects will meet with their therapist team for three preparatory sessions and two blinded experimental psychotherapy sessions of MDMA-assisted psychotherapy. One month after the second experimental session, the primary endpoint assessment will take place, after which the blind will be broken. Subjects who receive one of the active doses will receive a third open-label experimental session with similar procedures. Subjects who receive the active dose 2 during the first two experimental sessions will be given the option to increase their dose in the third experimental session to match the active dose 1 treatment group. Subjects who receive the comparator dose will be offered the option to continue to the open-label Stage 2 unless they meet any exclusion criteria for study participation. Stage 2 will be used to explore the optimal therapeutic dose of MDMA using a clinical titration dosing strategy. After a single preparatory

session, active dose 2 will be administered at the first session and the therapists will choose one of the two active doses of MDMA for the second and third experimental sessions, with an optional supplemental half dose at each of three experimental sessions at time points equivalent to those in Stage 1 (See Time and Events Table).

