9.1 Analysis Populations

Modified Intent-to-treat (mITT): all subjects who were randomized, received at least one experimental session and completed at least one outcome assessment

Per protocol (PP): all subjects who completed two experimental sessions and primary outcome assessment in Stage 1 and did not experience a major protocol deviation

Crossover: all subjects who completed Stage 2 in addition to completing Stage 1

Safety: all subjects who receive any study treatment

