9.9.4 Safety Analyses

The primary measure of safety will be the reporting of adverse events. The Adverse events considered are Treatment Emergent Adverse Events (TEAE) defined as those AE's that occurred after dosing and existing medical history diagnoses that worsened during the study. Verbatim terms on case report forms will be mapped to preferred terms and system organ classes using the MedDRA dictionary. For incidence reporting if a subject has more than one AE mapped to the same preferred term, that AE will be reported only once using the highest severity and closest relationship to study drug. Subject incidence of AEs will be displayed by Stage I treatment group and by system organ class. AEs will also be summarized by severity and relationship to study drug. Subject incidence of SAEs by Stage I treatment group will also be displayed. In addition to the listing of all AEs, a listing of SAEs and a listing of AEs leading to discontinuation of study drug will be included.

Summary tables of frequency listings of commonly reported AEs (Spontaneously Reported Reactions) mapped to preferred terms will be displayed during and after each experimental session by Stage 1 treatment group.

Columbia Suicide Severity Rating Scale (C-SSRS)

Suicidal ideation and behavior will be summarized according to suggestions made in the Columbia-Suicide Severity Rating Scale Scoring and Data Analysis Guide [2]. A positive response for suicidal ideation is counted when a subject answers "yes" to any one of the five suicidal ideation questions (Categories 1-5) on the C-SSRS, i.e. a score > 0 for suicidal ideation score. Serious suicidal ideation is a suicidal ideation score of 4 or 5. A positive response for suicidal behavior occurs when a subject answers "yes" to any one of the five suicidal behavior questions (Categories 6-10) on the C-SSRS, i.e. a score > 0 for suicidal behavior score. The number and percent of positive responses of Positive Ideation, Serious Ideation, and Positive Behavior will be tabulated by Stage I treatment group and time period. Compare lifetime serious suicidal ideation and positive behavior frequencies to cumulative frequencies anytime during the study until end of Stage 1 and Stage2.

Subjective Units of Distress (SUD)

Descriptive statistics for SUD scores will be calculated by Stage 1 treatment group and time period with counts and percentages.

Visual analog scale for Tinnitus and/or Pain visual analog scale

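### SAP 9.9.4 sets no end to the treatment-emergent period, so the AE and SAE tables by Stage I group can count open-label 100-125 mg events under 40 mg, and a Stage 1-only cut would set three active sessions against two

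*SAP*

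**What the plan says.** SAP 9.9.4 names adverse event reporting as the primary measure of safety. Treatment-emergent events are "defined as those AE's that occurred after dosing and existing medical history diagnoses that worsened during the study". That gives a start but no closing visit, day or stage. For incidence, if a subject has several events under one preferred term, "that AE will be reported only once using the highest severity and closest relationship to study drug". The columns are the randomised groups: "Subject incidence of AEs will be displayed by Stage I treatment group and by system organ class", and "Subject incidence of SAEs by Stage I treatment group will also be displayed". A further sentence says "AEs will also be summarized by severity and relationship to study drug", with neither a grouping nor a period.

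SAP 9.1 defines the population without reference to stage: "Safety: all subjects who receive any study treatment".

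Other displays in 9.9.4 do carry a time split. Spontaneously reported reactions are shown for each experimental session by group, distress scores by group and period, and the main C-SSRS counts "will be tabulated by Stage I treatment group and time period".

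On exposure, SAP 5.0 says "Subjects who receive one of the active doses will receive a third open-label experimental session with similar procedures". Protocol 5.2.7 gives comparator subjects no third Stage 1 session. Those who choose Stage 2 receive three open-label sessions, the first at 100 mg and the others at 100 or 125 mg (Protocol 5.2.9; Table 5 in 6.2.1).

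**The concern.** A table headed by randomised group will be read as a comparison of doses. With no closing date, a crossover subject's events at 100-125 mg appear in the 40 mg column. Counting once per term at worst severity and closest relationship also means that a mild event at 40 mg is replaced by a more severe one of the same kind at an active dose. This tends to hide a dose difference.

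A programmer who read Stage I as a period as well as a grouping would cut at the end of Stage 1. That gives the active groups an extra, open-label session and can create a difference. The two readings err in opposite directions, and the SAP does not choose between them. SAP 3.0 says the study is meant to yield effect size estimates for safety as well as efficacy and to feed a meta-analysis, so a mixed 40 mg column could be carried into pooled summaries.

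**Working it through.** **Does any other text close the period?**
- SAP 9.1: no stage limit on the Safety population.
- SAP 9.10: the primary efficacy analysis follows completion of Stage 2, so Stage 2 events are in the data by then.
- Protocol 8.5: limits what is collected (all AEs on the dosing day and for seven days afterwards, SAEs to termination, some classes in between). These rules run through both stages and assign no event to a column.
- Protocol 12.0: frequency tables of reactions and AEs, with no period.

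None supplies an end.

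**Sessions and cumulative MDMA per subject.** Inputs are the doses in Protocol Table 5, with all sessions completed. The lower figure has no supplemental doses and the upper has all of them.

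| Window | 40 mg column | 100 mg column | 125 mg column |
|---|---|---|---|
| First dose to visit 12 | 2 sessions; 2×(40 to 60) = 80-120 mg | 2; 2×(100 to 150) = 200-300 | 2; 2×(125 to 187.5) = 250-375 |
| Stage 1 only | 2; 80-120 | 3; 200-300 plus 100-187.5 = 300-487.5 | 3; 3×(125 to 187.5) = 375-562.5 |
| Whole study, Stage 2 completed | 5; 80-120 plus 300-525 = 380-645 | 3; 300-487.5 | 3; 375-562.5 |

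The Stage 2 amount is (100 to 150) + 2×(100 to 187.5) = 300-525 mg. Three of the five sessions (60%) are at an active dose. With supplemental use matched, the crossover subject exceeds the 125 mg column even without titration:
- No supplements: 80 + 300 = 380 v 375 mg.
- All supplements: 120 + 450 = 570 v 562.5 mg.

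With titration at both later sessions the totals are 430 and 645 mg. In both longer windows the 100 mg column may also contain a third session at the 125 mg level.

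**Illustration only.** The documents give no usable per-session risks. Let p be the assumed per-session risk at 40 mg and q the risk at an active dose. With independent sessions, subject incidence is:
- Visit 12: active 1-(1-q)², comparator 1-(1-p)².
- Stage 1 only: active 1-(1-q)³, comparator unchanged.
- Whole study: active 1-(1-q)³; a crossover subject 1-(1-p)²(1-q)³; the 40 mg column averages crossover and non-crossover subjects.

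At the other extreme, fully dependent sessions, a subject's risk is the highest per-session risk received. Active minus comparator, in percentage points, from dependent to independent:

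| Assumed p / q | To visit 12 | Stage 1 only | Whole study, 3 of 5 cross over | Whole study, all 5 cross over |
|---|---|---|---|---|
| 5% / 10% | +5.0 to +9.25 | +5.0 to +17.35 | +2.0 to +2.7 | 0.0 to -7.1 |
| 10% / 20% | +10.0 to +17.0 | +10.0 to +29.8 | +4.0 to +6.1 | 0.0 to -9.7 |

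For example, at 10%/20% with independent sessions and all five crossing over, the active column is 1-0.8³ = 48.8% and the 40 mg column is 1-0.9²×0.8³ = 58.5%.

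Session count alone also matters. With the same 20% per-session risk in every group and independent sessions, a Stage 1-only table shows 1-0.8³ = 48.8% against 1-0.8² = 36.0%. Cut at visit 12, every column reads 36.0%.

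**The case against.** The strongest reply is that little is affected. SAP 8.2 counts spontaneously reported reactions as adverse events, and 9.9.4 already shows them by group for each session. The tables are displayed, not tested; full AE and SAE listings are planned; SAP 9.6 reports dose timing and total mg by group; and Stage 2 is optional. All of this stands. It narrows the problem mainly to SAEs, AEs outside the listed reactions, and reactions that outlast seven days. It does not give the tables a window.

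It can also be said that three sessions against two is the trial's design, and that the SAP nowhere specifies a Stage 1-only table. That is fair. The imbalance is relevant only because the Stage 1-only cut is the obvious alternative and does not give a like-for-like comparison either.

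A reader might infer more than the documents support:
- That these are the only AE displays by group. They are not, given the reaction tables.
- That a crossover subject always has more MDMA than a 125 mg subject. The ranges overlap (380 mg without supplements is below 562.5 mg with them); the ordering holds at matched supplemental use.
- That observation time can be read off exactly. The 15 and 18 months in Protocol 4.1 appear to run from enrollment, not first dose, so only the three-month difference is usable. Counting eight collection days per session is one reading, because the SAP schedules also tick all AEs at visits 12, 17, 27 and 32.
- That the C-SSRS is untouched. Its main counts are split by period, but the cumulative comparison to the end of Stage 1 and Stage 2 states no grouping.

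**Conclusion.** The point holds. As written, SAP 9.9.4 places a crossover subject's events from three open-label active-dose sessions under 40 mg, and limiting the tables to Stage 1 leaves three sessions against two. Only first dose to visit 12 compares the groups over the same number of sessions, all blinded.

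The session counts and mg totals come from the documents and assume that all sessions are completed. The incidence figures rest on assumed risks and show direction only. The extent of the mixing depends on how many of the five planned comparator subjects cross over. If none does, the mixing is zero, but the table still sets three active sessions against two.

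A reader might conclude that safety data are lost or that a formal safety conclusion is invalid. Neither follows: the listings preserve the events and no test or decision rule uses these tables. The harm is a misleading summary of the named primary safety measure. That is worth correcting before the SAP is finalised, because choosing the window after seeing the data would mean choosing between tables that favour different conclusions.

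**What to change.** In SAP 9.9.4:
- State that the between-group AE and SAE incidence tables, and the severity and relationship summaries, cover first dose to visit 12/unblinding by randomised group.
- Tabulate later events separately by dose received: the third Stage 1 session, Stage 2, and follow-up. Show comparator subjects who decline Stage 2 under 40 mg.
- Label the reaction tables Stage 1 or Stage 2, since session numbers 1 to 3 are used in both stages.
- If the C-SSRS cumulative comparison is shown by group, apply the same split.

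The cost is SAP wording and a few extra tables; dose timing and total mg are already to be summarised under SAP 9.6. Trial conduct does not change. The drawback is small counts: with five planned comparator subjects, one subject is 20 percentage points.

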2.4 Rationale of Dose Selection

This study will compare the effects of psychotherapy sessions assisted by either one of two active doses of MDMA or a comparator dose. The active dose 1 will be 125 mg MDMA followed 1.5 to 2.5 hours later by an optional supplemental dose of 62.5 mg MDMA. The active dose 2 will be 100 mg MDMA followed 1.5 to 2.5 hours later by an optional supplemental dose of 50 mg MDMA. The comparator dose will be 40 mg MDMA followed 1.5 to 2.5 hours later by an optional supplemental dose of 20 mg MDMA. Eighteen of 23 subjects, or 78%, will be assigned to one of the active dose conditions, and five of 23, or 22%, will be assigned to the comparator dose condition. The active dose 1 is equal to the full dose in other MAPS-supported MDMA/PTSD studies.

Subjects in the comparator dose condition during Stage 1 will have the opportunity to cross over to Stage 2. Stage 2 will be used to explore the optimal therapeutic dose using a clinical titration dosing strategy in the second and third Stage 2 sessions allowing for a

choice between two different active doses of MDMA. In Stage 2 subjects will receive an initial dose of 100 mg followed 1.5 to 2.5 hours later by an optional supplemental dose of 50 mg MDMA during the first experimental session. In the second and third session they will receive an initial dose of 100 mg or 125 mg MDMA followed 1.5 to 2.5 hours later by an optional supplemental dose of 50 mg or 62.5 mg, respectively. The decision to titrate the dose in the second and third session will be based on the experience of the first session. If 100 mg MDMA does not seem to be the optimal therapeutic dose based on the first experimental session in Stage 2, the dosage may be increased by an increment of 25 mg in order to achieve the optimal therapeutic dose. The supplemental doses for each experimental session will be half of the initial dose, respectively. The same choice will be provided to Active Dose 2 subjects continuing on to receive a third experimental session in Stage 1 in an open label context.

Table 1. Dose Regimen

Dose	Initial Dose	Optional Supplemental Dose	Min-Max Cumulative Dose	Min-Max Cumulative Dose with Titration
Active Dose 1	125 mg	62.5 mg	125-187.5 mg	N/A
Active Dose 2	100 mg	50 mg	100-150 mg	N/A
Active Dose 2	100 mg	50 mg	100-150 mg	N/A
+ Optional Titration Dose	25 mg	12.5 mg	N/A	125-187.5 mg
Comparator Dose	40 mg	20 mg	40-60 mg	N/A

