The active dose 1 of MDMA to be used in this study is identical to the full dose used in previous studies in the U.S., Switzerland, and Israel. Previous researchers have also used doses within this range [63, 64, 66, 68, 109-114]. Prior to the scheduling of MDMA, similar doses and regimens were used in psychotherapy [50, 52, 55]. The initial active doses are expected to produce all the commonly reported effects of MDMA, including changes in affect, mood, and cognition and changes in feelings of interpersonal closeness and trust. The supplemental dose will prolong subjective drug effects without producing physiological effects any greater than peak effects occurring after the initial dose.

The doses to be compared in this study have been chosen on the basis of the Sponsor’s ongoing initiative to develop a dose response curve of MDMA-assisted psychotherapy in the treatment of PTSD. They are very similar to doses used in Phase 1 studies [64, 69]. This dose is expected to produce increases in positive mood and tension, in combination with a lower degree of therapeutic effects than the active doses.

The 100 mg MDMA initial dose will be administered in the first experimental session in Stage 2. Prior to both the second and third experimental sessions in Stage 2 the co-therapists, in consultation with the subject, will decide whether the same dose or an initial dose of 125 mg (each with the corresponding optional supplemental dose) would be more likely to constitute the optimal therapeutic dose for each of these experimental sessions.

During the third experimental session in Stage 1, subjects who receive the 100 mg MDMA initial dose will also have this consultation.

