The sponsor will collect Changes in Tinnitus and/or Pain visual analog scale scores from any subject reporting tinnitus or chronic pain during each point of administration, including baseline, experimental and integrative sessions, the primary endpoint, and two-month follow-up. The sponsor will plot out and examine all changes in tinnitus and/or pain visual analog scale scores across both groups and in each active dose group and the comparator dose group for trends. Formal analysis of changes in tinnitus and/or pain visual analog scale scores will only occur if three or more subjects complete changes in tinnitus and/or pain visual analog scale at baseline and primary endpoint. Likewise, formal between-groups analyses will not be performed if all primary endpoint scores are from subjects assigned to the same condition. The sponsor will perform an independent t-test on the difference between baseline and primary endpoint Changes in Tinnitus and/or Pain visual analog scale scores between each active dose and comparator dose conditions, with p. set at 0.05. If the only scores available are for subjects in a single condition, then a paired t-test will be performed comparing baseline and primary endpoint Changes in Tinnitus and/or Pain visual analog scale scores, with p. set at 0.05.

Perception of the experimental sessions will be examined during Stage 1 and Stage 2, before and after subjects have undergone a third experimental session. The results of this exploratory analysis will inform the sponsor of expectancies and the value of the third session for future protocol development. These data may be correlated with primary/secondary endpoint CAPS data compared to end of Stage 1/Stage 2 CAPS data to assess the potential contribution of expectation and self-reported response to changes in PTSD symptoms.

The sponsor will compare CAPS, PDS, PTGI, GAF, BDI-II, PSQI, and DES-II, scores at the final two-month follow-up assessment to the 12-month follow-up using difference scores in an independent t-test for a within-subject analysis with p value set at 0.05.

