3.0 Background

This Phase 2 pilot study will examine the safety and efficacy of manualized MDMA-assisted psychotherapy in subjects with chronic, treatment-resistant PTSD of at least six months duration who were unable to achieve remission despite having received prior treatment with either pharmacotherapy or psychotherapy of adequate dose/duration or who discontinued treatment due to lack of tolerability. Two active doses of MDMA (125mg and 100mg) and a comparator dose (40mg) will be assessed in Stage 1, as will the benefit of three versus two active dose sessions. Subjects who received the 100mg dose in their first two Stage 1 experimental sessions will be given the option to titrate up to 125mg in their third Stage 1 experimental session. Subjects who received the comparator dose during Stage 1 will have the opportunity to cross over and take part in a second study segment, referred to as Stage 2, with three open-label experimental sessions. Stage 2 will be used to explore the optimal therapeutic dose of MDMA using a clinical titration dosing strategy. Two types of co-therapist teams will conduct the study. Each team will have an experienced therapist with a background consistent with that required in the treatment manual paired with either another experienced therapist or an “intern” co-therapist that is either pre-licensure, is licensed but with less experience, has a different therapy background than indicated in the manual, or practices a different healing profession (physician, nurse, social worker).

This study is designed to obtain estimates of effect size for safety and efficacy. The data will be combined with ongoing Phase 2 dose response studies in a meta-analysis. Cognitive function will also be assessed at baseline, one month after the second experimental session and two months after the third experimental session with active dose MDMA. This study is also intended to continue the development of a manualized psychotherapeutic approach to this potential treatment.

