6.0 Randomization and Blinding

Per Amendment 6, 26 subjects will be enrolled into the study. The randomized portion of the study will be blinded and there will be a 12:9:5 ratio between subjects in the active dose 1, active dose 2, and comparator dose treatment groups. Subjects will be assigned subject numbers, and subjects will be randomized in a blinded fashion.

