Formal analysis of Changes in Tinnitus and/or Pain visual analog scale scores will only occur if three or more subjects complete Changes in Tinnitus and/or Pain visual analog scale at baseline and primary endpoint. Likewise, formal between-groups analyses will not be performed if all primary endpoint scores are from subjects assigned to the same treatment group. Descriptive statistics will be presented on the difference between baseline and primary endpoint changes in Tinnitus and/or Pain visual analog scale scores in the full dose and comparator dose treatment groups.

Vital signs

Vital signs (heart rate, body temperature, systolic and diastolic blood pressure) will be summarized using descriptive statistics at baseline and at each post-baseline time point. Occurrences of systolic and diastolic blood pressure, heart rate, and body temperature readings above the pre-determined cutoff will be displayed with numbers and percentages by timepoint.

Paced Auditory Serial Addition Test (PASAT) and Repeatable Battery for the Assessment of Neuropsychological Status (RBANS)

RBANS and PASAT scores at baseline and primary endpoint will be compared in each active dose group and comparator dose groups using descriptive statistics. In an exploratory analysis, the effects of maximal exposure to MDMA on neurocognitive function using the RBANS and PASAT will be examined.

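### SAP 9.9.4 words the tinnitus/pain change summary for two dose groups in a three-arm trial; read literally, the 100 mg arm is left out of that summary

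*SAP*

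**What the plan says.** SAP 9.9.4, in the paragraph on the tinnitus/pain visual analog scale, sets conditions for a formal analysis. It then says that descriptive statistics on the difference between baseline and primary endpoint will be presented "in the full dose and comparator dose treatment groups".

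The design has three groups. SAP 3.0 says: "Two active doses of MDMA (125mg and 100mg) and a comparator dose (40mg) will be assessed in Stage 1". SAP 6.0 says: "there will be a 12:9:5 ratio between subjects in the active dose 1, active dose 2, and comparator dose treatment groups".

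The SAP uses the term *full dose* in this sentence and does not define it. Protocol 2.4 mentions it twice in connection with this trial's doses: "The active dose 1 is equal to the full dose in other MAPS-supported MDMA/PTSD studies", and "The active dose 1 of MDMA to be used in this study is identical to the full dose used in previous studies".

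For the same measure, Protocol 12.0 plans plots for each active dose group and for the comparator. It also plans an independent t-test on the baseline-to-endpoint difference "between each active dose and comparator dose conditions".

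**The concern.** The sentence has the form of a two-arm trial. If *full dose* carries the only meaning the protocol gives it, the table has a 125 mg column and a 40 mg column and no place for 100 mg. SAP 9.0 keeps data that the plan does not analyse out of tables and graphs and sends them to listings. The 100 mg values would then be listed but not summarised.

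The scale is listed among the safety measures in SAP 8.2, and the study is described as a dose-response study. Omitting the middle dose would mean that this table could not show how change varies across the three doses, and that the SAP presents less than the protocol promised without giving a reason.

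**Working it through.** This is mainly a comparison of texts. The only arithmetic concerns arm sizes.

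**1. Planned arm sizes.** SAP 6.0 gives 12:9:5 and states the total: "Per Amendment 6, 26 subjects will be enrolled into the study". Check: 12 + 9 + 5 = 26, which agrees. Protocol 5.3 has 9:9:5 (total 23). The 100 mg arm is 9 under either allocation.

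**2. Groups named for this measure and its neighbours.**

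| Place | Measure | Groups |
|---|---|---|
| Protocol 12.0 | Tinnitus/pain scale, plots | Each active dose and comparator |
| Protocol 12.0 | Tinnitus/pain scale, t-test | Each active dose against comparator |
| SAP 9.9.4 | Adverse events, C-SSRS, SUD | Stage 1 treatment group |
| SAP 9.9.4 | RBANS and PASAT | Each active dose and comparator |
| SAP 9.9.4 | Tinnitus/pain scale | Full dose and comparator |

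Of these SAP 9.9.4 summaries, only the last names two groups.

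**3. The two possible meanings of *full dose*.**

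- *It means 125 mg.* This is the only link the documents make. The summary then covers 12 + 5 = 17 of 26 planned subjects and leaves out the 9 in the 100 mg arm.
- *It is shorthand for both active doses.* No arm is lost, but the sentence then describes one active group against the comparator, whereas Protocol 12.0 treats each active dose separately. The SAP does not say whether the doses would be pooled.

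The sentence departs from the protocol on either meaning.

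**4. How many subjects this affects.** The omitted arm is 9/26 = 35% of planned enrolment, and 9/(12 + 9) = 9/21 = 43% of planned active-dose subjects. These are shares of whole arms. Only subjects with pre-existing tinnitus or chronic pain complete the scale, and the documents do not say how many there are in any arm. On planned enrolment the number of 100 mg subjects whose values would be missing from the summary lies between 0 and 9. Actual denominators may also differ from plan, because SAP 9.3 keeps two replaced withdrawals in the Safety and mITT populations.

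**The case against.** The strongest reply is that this is a loose label and not an exclusion. Five arguments support it.

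- **The term is undefined for this trial.** Protocol 2.4 says what the full dose was in other studies; here the groups are active dose 1, active dose 2 and comparator. Carried-over two-arm wording, or shorthand for active dosing, would explain the phrase as well as a decision to drop an arm. This stands. A reader might infer that the sponsor chose to exclude 100 mg from the safety review of this measure, but nothing in the documents supports that. The three-group wording around the sentence points to a drafting slip.

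- **Other SAP text may cover the arm.** SAP 9.9 promises descriptive statistics by treatment group for primary, secondary and exploratory endpoints, and Protocol 5.1.2 calls this scale exploratory. This is arguable but does not settle the matter: SAP 8.2 lists the scale as a safety measure, and the specific sentence in 9.9.4 is narrower than the general one.

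- **The conditions for formal analysis are not limited by dose.** A 100 mg subject counts towards the minimum of three, so one can dispute that these values fall under the listings-only rule. This stands in part. However, the SAP names neither a test nor groups for that formal analysis, so the two-group summary is the only output it specifies. Listings-only is the consequence of a literal reading, not something the SAP states.

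- **The safety objective is not breached.** A reader might conclude that a stated objective goes unanswered for one arm. SAP 4.3 asks only that these changes be collected, and they are collected in every arm. The per-dose requirement comes from Protocol 12.0, not from the objective.

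- **There is a partial backstop.** Treatment-emergent adverse events include worsening of existing medical history diagnoses and are shown by Stage 1 treatment group, so worsening recorded as an adverse event at 100 mg would still be tabulated. This also stands, within the limits of the adverse-event collection windows.

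**Conclusion.** The sentence is wrong as written. It names two groups in a three-arm trial, uses a term the SAP does not define, and departs from Protocol 12.0 on either meaning of that term. On the only meaning the documents support (125 mg), the 100 mg arm is left out of the summary and its values go to listings.

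The size is small. The number of subjects affected is unknown, between 0 and the 9 planned at 100 mg. The effect is limited to one descriptive safety summary; no primary or secondary efficacy result depends on it. It would be tempting to report 35% or 43% as the share of data lost, but the documents do not support that, because those figures count whole arms and not subjects with tinnitus or chronic pain.

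The conclusion assumes that the specific sentence in SAP 9.9.4 takes precedence over the general statement in SAP 9.9.

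**What to change.** In the tinnitus/pain paragraph of SAP 9.9.4, replace the two-group phrase with: *in each Stage 1 treatment group (active dose 1, active dose 2, comparator) and overall*. This matches Protocol 12.0 and the neighbouring summaries in the same SAP section, and removes the undefined term.

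The cost is one phrase in the SAP and the corresponding table shell. No new data, visits or subjects are needed.
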